#### 9.4.15. Change from Baseline in Number of Tender Joints or Swollen Joints

The number of joints (via Tender and Swollen Joint Counts assessment eCRF) are scheduled to be assessed at Screening, Weeks 6, 14, 20, 24, 36, 44 and Week 52/End of Study/Early Termination Visit, Post-treatment Follow-up Month 3, and Post-treatment Follow-up Month 6.

Observed values and change from baseline in the number of joints identified as tender or swollen at each scheduled visit will be summarized using descriptive statistics (i.e. n, mean, standard deviation, median, minimum, and maximum). Changes from baseline for the number of joints to each visit and overall will be analyzed with an MMRM ANCOVA model as described in Section 9.4.

#### 9.4.16. Change from Baseline in Physician Global Assessment of Gout

The physician global assessment will be collected at the Screening and Week -6 (prior to the first dose of MTX) Visits; prior to pegloticase infusion at the Day 1 and Weeks 6, 14, 20, 24, 30, 36, and 44 Visits during the Pegloticase + IMM Period; at the End of Pegloticase Infusions Visit (if

This document is confidential.

applicable), and the Week 52/End of Study/Early Termination Visit. The global assessment asks the physician to respond to the statement, "Considering the subject's overall health related to gout, rate their gout overall" using a numeric rating scale ranging from 0 (excellent) to 10 (very poor).

Observed values, change from baseline in the physician global assessment at selected scheduled time point will be summarized using descriptive statistics (i.e. n, mean, standard deviation, median, minimum, and maximum). Changes from baseline for the physician global assessment to each visit and overall will be analyzed with an MMRM ANCOVA model as described in Section 9.4.

#### 9.4.17. Gout Chronic Response

Gout chronic response (GCR) criteria will be used to define subjects who achieve 20%, 50%, or 70% improvement in 3 of the 4 following measures at a scheduled time point:

- swollen joint count
- tender joint count
- HAQ health score
- HAQ pain score

The GCR response will be determined at Week 14, Week 24, Week 36, End of Pegloticase Infusion Visits, Week 52/End of Study/Early Termination Visit, Post Treatment Follow-up Month 3, and Post-treatment Follow-up Month 6.

A subject will be defined as a GCR20 (GCR50, GCR70) responder at a post-baseline assessment if they have at least a 20% (50%, 70%) reduction from the baseline in 3 or more of the measures noted above. If a subject has 3 of the 4 measures and all 3 meet the reduction goal, the subject will be a responder. In addition, if a subject has value of zero at baseline and also value of zero at the given post baseline for any tests above, the subject is considered to have at least 20%, 50%, and 70% reduction from the baseline for that assessment.

In the other cases, including subjects with fewer than 4 of the criteria completed at the scheduled assessment, and subjects with all 4 criteria completed at the scheduled assessment who do not meet the 20% (50%, 70%) reduction criteria, subjects will be declared non-responders at the scheduled assessment.

GCR20, GCR50, and GCR70 responses, and the number/percentage of subjects who achieved a 20%, 50%, and 70% reduction in each component endpoint in the GCR response, will be summarized and the difference between treatment groups will be analyzed using the same stratified weighting approach specified for primary analysis.

Considering some subjects also have tophus area at baseline, another analysis with the same CMH test is proposed. A subject will be defined as a GCR20 (GCR50, GCR70) responder at a post-baseline assessment if they have at least a 20% (50%, 70%) reduction from baseline (including subjects who have zero value at baseline and zero at the given post baseline in 4 or more of the measures noted above including tophus area).

This document is confidential.

#### 9.4.18. Change from Baseline in SBP and DBP

Routine vital signs, including blood pressure, respiratory rate, temperature, and heart rate will be measured at Screening, Week -6, Week -4, Day 1 and Weeks 2, 4, 6, 8, 10, 12, 14, 16, 18, 20, 22, 24, 26, 28, 30, 32, 34, 36, 38, 40, 42, 44, 46, 48, 50 and the End of Pegloticase Infusions Visit (if applicable), Week 52/End of Study/Early Termination and 3 and 6 month Post Treatment Follow-up Visits. Elevated levels of SUA are associated with an increased risk of hypertension [Johnson et al, 2109], so reducing SUA levels may decrease SBP and DBP over time.

Observed values and change from baseline in SBP and DBP at each scheduled time point will be summarized using descriptive statistics (i.e. n, mean, standard deviation, median, minimum, and maximum). Changes from baseline for SBP and DBP to each visit and overall will be analyzed with a MMRM ANCOVA model as described in Section 9.4.

### 9.5. Other Efficacy Endpoints and Analyses

#### 9.5.1. Investigator Assessment of Clinical Status

At the Week 24, End of Pegloticase Infusion Visit (if last infusion occurred earlier than Week 50), and Week 52 / Early Termination visit, the investigator will assess the following items related to gout:

- Current clinical status
  - Presence of tophi
  - Notable tophi characteristics
- Presence of chronically swollen joints due to gout (yes/no)
- Presence of chronic joint pain attributed to gout (yes/no)
- Symptoms the patient is specifically seeking to improve (yes/no)
  - Tophi presence / size
  - Physical function due to tophi
  - Frequency of flares
  - Chronic joint swelling attributed to gout
  - Chronic joint pain attributed to gout
  - Other symptoms

The responses to the questions will be summarized descriptively by visit. The number of symptoms seeking to improve will be summarized with descriptive statistics. The clinical status assessment will be presented in a listing.

## **10. Analysis of Anti-Drug Antibodies and Pharmacokinetics**

### **10.1. Anti-Drug Antibodies**

Serum samples for evaluation of anti-PEG and anti-uricase IgG antibodies will be collected prior to the pegloticase infusion on Day 1 and at the Weeks 2, 6, 14, 22, 24, 36, and at the non-infusion End of Pegloticase Infusions Visit (if applicable) or the Week 52/End of Study/Early Termination Visit and Month 3 Post Treatment Follow-up Visits.

Using the Safety Population for anti-PEG IgG antibodies, the number and percentage of subjects ADA positive and ADA negative at baseline will be summarized. Additionally, the number and percentage of subjects who meet the following criteria will be summarized by scheduled timepoint and treatment group:

- ADA positive in subjects ADA negative at baseline or with increase in titer from baseline,
- ADA positive in subjects ADA negative at baseline, and
- ADA positive in subjects with increase in titer from baseline

For anti-uricase IgG antibodies, the number and percentage of subjects ADA positive at baseline and post-baseline will be summarized by scheduled timepoint and treatment group.

Kaplan-Meier estimates of the time to positive anti-PEG response (for subjects who were negative at baseline) or increase in anti-PEG titer (for subjects who were positive at baseline), and the time to anti-uricase response with 25th percentile, median, 75th percentile, and 95% CI, along with a Kaplan-Meier curve will be produced by treatment group. Subjects who never have a positive anti-PEG response or increase in titer will be censored at the date of their last visit (Week 52/End of Study/ET visit, or, if the subject did not attend this visit, then whatever last visit they have on record).

Anti-PEG and anti-uricase titer will be summarized descriptively with mean and CV% by study visit.

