In a post-hoc analysis, the apparent role of immunogenicity in both loss of urate lowering effect and incidence of infusion reactions was appreciated. Only 2% of subjects with anti pegloticase antibody titers exceeding 1:2430 maintained a urate-lowering response to pegloticase compared with 63% of subjects who were treated for at least 2 months without developing high-titer antibodies ( $p < 0.001$ ) (Sundy et al., 2011). The incidence of IRs was higher among subjects who developed high-titer antibodies compared with those who had titers that did not exceed 1:2430 (60% vs 19%;  $p < 0.001$ ) (Sundy et al., 2011). In addition, most IRs occurred when sUA levels were greater than 6 mg/dL. Retrospective analyses showed that the loss of urate-lowering efficacy, as reflected by sUA of greater than 6 mg/dL, preceded a patient's first IR, whenever it occurred, in 20 (91%) of 22 subjects treated with pegloticase every 2 weeks.

Reducing anti-drug antibodies with concomitant administration of the immunomodulatory agent methotrexate (MTX) has been shown to be useful with other infused products that lead to immunogenicity, such as adalimumab, in the setting of rheumatoid arthritis treatment [Burmester GR, Kivitz AJ, Kupper H, 2015]. This study will test whether the loss of sUA response to pegloticase can be prevented or delayed by the pre-treatment and concomitant use of MTX with pegloticase compared to pegloticase alone.

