## 7.2 Rationale for this Study

Immunogenicity (anti-pegloticase antibodies) in response to pegloticase therapy may lead to loss of therapeutic response and/or AEs, including IRs. In the phase 3 studies, IRs occurred more commonly in subjects whose sUA values increased above 6 mg/dL, after initially showing response following the first 1 or 2 infusions. The titer of the anti-drug antibody was also associated with loss of response, with subjects having the highest levels of anti-drug antibodies showing the lowest response rates.

The development of anti-drug antibodies can be influenced by drug and treatment-related factors, as well as patient characteristics. A potential prophylactic strategy to manage anti-drug antibody response with pegloticase is the co-administration of immunomodulatory therapy. Various methods are used to reduce antibody production in other settings, the most common of which is the use of traditional rheumatoid arthritis disease-modifying drugs, such as MTX, azathioprine,

mycophenolate mofetil, leflunamide, and others, as is commonly implemented with rheumatoid arthritis biological therapy (e.g., infliximab and other infusible and subcutaneous antibody products) [Strand et al, 2017].

MTX is the most commonly used non-biological disease modifying agent worldwide and is frequently used in combination with other biological therapies [Strand et al, 2017].

In the current study, MTX will be evaluated for its ability to improve the response rate and reduce IRs with pegloticase by reducing drug immunogenicity. Prospective use of sUA stopping rules, with pegloticase treatment cessation (but study continuation) when a subject has an sUA level > 6 mg/dL on two consecutive study visits, will also help confirm the value of this approach to reduce IR risk.

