### 9.6.6 Pharmacokinetic and Anti-drug Antibody Analysis

Concentrations for pegloticase and MTX polyglutamate (as appropriate) will be summarized using descriptive statistics for the PK population. Details will be provided in a separate PK analysis plan.

Incidence of anti-drug antibodies and titer levels will be summarized.

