#### **4.4. Pharmacokinetic and Anti-drug Antibody Endpoints**

The PK and anti-drug antibody endpoints are:

- PK of pegloticase.
- MTX polyglutamate concentrations.
- The incidence of anti-PEG and anti-uricase IgG antibodies.

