## **6. General Aspects for Statistical Analysis**

### **6.1. General Methods**

The following conventions will be utilized in the analyses:

- In general, descriptive summaries will be provided. Efficacy summaries will be provided showing columns for the treatment of Pegloticase + MTX, or Pegloticase + Placebo for the ITT, mITT, and PP populations. Safety summaries will be provided for the safety population. For safety summaries during the MTX Tolerability Assessment Period, the MTX population will be used. Depending on the treatment period, different columns will be presented for safety summaries:
  - single column of MTX will be presented for MTX tolerability assessment period;
  - columns of MTX or Placebo will be presented for Run-in Period;
  - columns of Pegloticase + MTX, or Pegloticase + Placebo will be presented for Pegloticase + IMM Period.
- The following labels will be used for the populations: "ITT Population", "mITT Population", "PP Population", "Safety Population", "MTX Population", or "PK Population". The following column labels will be used for the treatment groups: MTX, Placebo, Pegloticase + MTX, or Pegloticase + Placebo.
- Unless otherwise indicated, continuous variables will be summarized using the number of observations (n), mean, standard deviation (SD), median, minimum (min), and maximum (max). Categorical variables will be summarized using number of observations (n), frequency and percentages of subjects.
- The same number of decimal places as the raw data will be presented when reporting min and max, 1 more decimal place than in the raw data will be presented when reporting mean and median, and 2 more decimal places than in the raw data will be presented when reporting SD.
- Unless otherwise specified, confidence intervals (CI) will be based on 95% confidence and two-sided.
- If multiple assessments occur at a given post-baseline time point, the latest value will be used.
- All relevant subject data will be included in listings. All subjects entered into the database will be included in subject data listings.
- Additional programming considerations are provided in Section 13.

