### **10.2. Pegloticase and MTX PK**

For all subjects, serum samples for PK analysis of pegloticase will be collected after the end of infusion on Day 1 (prior to discharge); prior to the pegloticase infusion and after the end of infusion (prior to discharge) at the Weeks 2, 6, 14, 21, 24, 36, End of Pegloticase Infusions Visit (if applicable) and Week 52/End of Study/Early Termination Visits. NOTE: Week 21 Visit and the End of Pegloticase Infusions Visit (if applicable) and Week 52/End of Study/Early Termination Visits are non-infusion visits.

Blood samples for MTX polyglutamate analysis will be collected prior to the pegloticase infusion on Day 1 and at the Weeks 14, 24 and 36 Visits during the Pegloticase + IMM Period .

The following presentations of subject pegloticase and MTX polyglutamate concentration data covered in this SAP will be provided:

This document is confidential.

- A listing including subject, week/time point (actual, planned), treatment and serum concentrations. End of infusion sampling times are expressed relative to the start time of infusion.
- A table summary of pegloticase and MTX polyglutamate concentrations at each time point (n; mean, SD, coefficient of variation (CV)% calculated as  $100\% \times SD/mean$ , minimum, 25th percentile, median, 75th percentile and maximum) for the PK Population or MTX Population, respectively.

Concentrations below the limit of quantification (BLQ) collected on Day 1 pre-dose will be summarized as zero. For the summary of pegloticase concentrations, all other concentrations BLQ will be imputed as half of the lower limit of quantification value. For the summary of MTX polyglutamate concentrations, all post-baseline concentrations BLQ will be excluded from analysis. The number of BLQ values will be presented for pegloticase and MTX summaries.

Concentrations for pegloticase will be summarized by treatment group for the PK Population. Further, the mean and CV% of pegloticase concentrations will be provided by visit and by treatment group in the subset of subjects who are ADA positive (defined as positive for anti-PEG or anti-uricase antibodies at any visit during the study) and ADA negative (defined as negative for both anti-PEG and anti-uricase antibodies for all visits during the study) for each visit.

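### The antibody titer table uses a mean and CV%, so a few very high titers can hide or reverse an MTX effect on titer level; a log-scale summary would largely avoid this

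*SAP*

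**What the plan says.** SAP 10.1 gives the height of the titer one sentence: "Anti-PEG and anti-uricase titer will be summarized descriptively with mean and CV% by study visit". It names no geometric mean, log scale, median, quartiles or high-titer category, and it does not say what value a negative sample takes. Nor does it say that the mean is arithmetic. The only definition of CV% is in SAP 10.2, for the concentration tables: "coefficient of variation (CV)% calculated as" 100% times SD over mean, which is the raw-scale formula. For concentrations, 10.2 also asks for quartiles, median, minimum and maximum and has rules for values below quantification.

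The named antibody endpoint (SAP 4.4) is "The incidence of anti-PEG and anti-uricase IgG antibodies". Protocol 9.6.6 says "Incidence of anti-drug antibodies and titer levels will be summarized" and names no statistic.

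The protocol's background gives weight to how high the titer is. Section 7.1.2 reports: "Only 2% of subjects with anti pegloticase antibody titers exceeding 1:2430 maintained a urate-lowering response to pegloticase". The comparison figure is 63% among subjects treated for at least 2 months without high titers, and infusion reactions were 60% against 19%. Section 7.2 adds: "The titer of the anti-drug antibody was also associated with loss of response".

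**The concern.** If outcome depends on how high the titer goes, the reader will want to see whether MTX lowers it. Positivity and time to response cannot show that, because a subject at 1:30 and one at 1:65,610 can count the same. For anti-PEG, SAP 10.1 also counts subjects whose titer rose from baseline, but only as yes or no. For anti-uricase it plans positivity and time to response, so the mean-titer sentence is the only planned description of level.

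On a scale of multiplicative steps, the arithmetic mean is driven by the upper tail, and CV% on that scale says little beyond the fact that the data are skewed. What is at stake is the between-arm reading of titer level at each visit. There is also no rule for negatives, so the mean could cover all subjects or only positives, and those answer different questions.

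**Working it through.** **Arm sizes.** The plan gives no figure for titers. Its sample-size statement (SAP 3.6) supplies the arm sizes, so it was checked first: 90 v 45, 71% v 43%, two-sided alpha 0.05.

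- Pooled proportion = (63.9 + 19.35)/135 = 0.617.
- SE under the null = √(0.617 × 0.383 × (1/90 + 1/45)) = 0.0888.
- SE under the alternative = √(0.71 × 0.29/90 + 0.43 × 0.57/45) = 0.0879.
- Power = Φ((0.28 − 1.96 × 0.0888)/0.0879) = Φ(1.21) = 88.6%, against the stated 88%. It reproduces.

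**Scale.** 2430 = 10 × 243 = 10 × 3⁵, which fits a 3-fold serial dilution starting at 1:10. The documents do not state the dilution scheme, so this is an inference.

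**Worked example (assumed titers).** All 45 placebo subjects are at 270. On MTX nearly everyone is one step lower, at 90, with one or two subjects at 65,610 (10 × 3⁸).

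- One high subject: mean = (89 × 90 + 65,610)/90 = 73,620/90 = 818 v 270, so the order is reversed. CV is 844%.
- Two high subjects: mean = (88 × 90 + 2 × 65,610)/90 = 139,140/90 = 1,546 v 270. CV is 628%, and the two subjects carry 131,220/139,140 = 94% of the sum.
- Geometric mean with two high subjects: 90 × 729^(2/90) = 104 v 270. Median: 90 v 270. Both keep the right direction.

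**Simulation.** Titer = 10 × 3^k, with k normal, rounded to whole steps and floored at 0; mean k is 4 on placebo and 3 on MTX (a 3-fold reduction); equal SD in both arms; 90 v 45; 20,000 trials per setting. With equal spread the underlying arithmetic mean is also lower on MTX, so a wrong ranking is sampling noise from the upper tail.

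| SD (steps) | 1 | 1.5 | 2 | 2.5 |
|---|---|---|---|---|
| Arithmetic mean ranks arms wrongly | 0% | 2.1% | 11.7% | 22.8% |
| Geometric mean ranks arms wrongly | 0% | 0% | 0.4% | 1.7% |
| Median ranks arms wrongly (ties not counted) | 0% | 0% | 0.4% | 1.2% |
| Share of MTX sum from the two highest titers | 13% | 28% | 42% | 54% |
| Typical CV% on MTX | 130 | 235 | 326 | 411 |

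**Variations.**

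- A smaller true effect, half a step (3^0.5 = 1.7-fold): the arithmetic mean is wrong in 2.7%, 16.5%, 29.6% and 38.7% of trials, and the geometric mean in 0.5%, 4.1%, 9.1% and 14.2%.
- A separate run with 97 v 48 subjects (the 145 in SAP 3.6 split 2:1) and k capped at 12 gave 2.2%, 11.4% and 21.7% for the arithmetic mean at SD 1.5, 2 and 2.5. At SD 2 the 95% range of the arithmetic-mean ratio was 0.06 to 1.96, against 0.17 to 0.73 for the geometric-mean ratio.

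**The case against.** A reader might infer that the trial's evidence on immunogenicity as a whole is compromised. The documents do not support that. The endpoint is incidence. SAP 10.1 gives positivity by timepoint and treatment group, and Kaplan-Meier time to antibody response by treatment group. SAP 11.3.1 relates adjudicated infusion reactions to antibody status. None of these uses mean titer.

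A reader might also infer that one or two titers must set the result. That depends on a spread the documents do not give. At an SD of one step the top two titers carry 13% of the sum and the arithmetic mean does not mis-rank. Even at 2.5 steps it has the right direction in about 77% of trials (100 − 22.8). The worked example is deliberately extreme.

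Three further points stand in part.

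- SAP 6.1 makes median, minimum and maximum the default for continuous variables unless the text says otherwise, and it sets arm columns for safety summaries. The titer sentence reads as replacing those statistics, and it omits the arm split that neighboring sentences state. Either may be a wording gap, and the blacked-out table index cannot settle it.
- Both the arithmetic mean and the 3-fold step are inferences. The 1:2430 figure comes from phase 3 titers against pegloticase, whereas this trial reports anti-PEG and anti-uricase separately.
- A geometric mean needs a value for negative samples, and the simulation did not test negatives. If many samples are negative, that choice could drive the result.

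**Conclusion.** The point holds for the titer table and no further. On the natural reading, the plan summarizes a multiplicative scale with a raw-scale mean and CV%. Given a true 3-fold reduction, that mean ranks the arms wrongly in about 0% to 23% of trials over SDs of 1 to 2.5 steps, against 0% to 1.7% for the geometric mean. The size rests on the assumed 3-fold steps, equal spread in both arms, the assumed SD range and the absence of negatives. The table is descriptive and has no role in testing, so no primary or secondary conclusion is at risk. The change is still worth making: it replaces a stated method with a better one at little cost, and the protocol itself ties titer height to loss of response and infusion reactions.

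**What to change.** In SAP 10.1, replace the mean and CV% for both antibodies, by treatment group and visit, with:

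- geometric mean titer with a 95% CI computed on log titer, median, quartiles and range;
- the MTX/placebo geometric mean ratio with 95% CI;
- the number and percentage above 1:2430, if this trial's assays report on a scale comparable with the phase 3 one.

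State the value assigned to negative samples and report how many there are. Keep the median beside the geometric mean, because the latter depends on that value.

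The cost is SAP wording, minor programming and one convention for negatives; no new samples are needed. The table remains descriptive.

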### **10.2. Pegloticase and MTX PK**

For all subjects, serum samples for PK analysis of pegloticase will be collected after the end of infusion on Day 1 (prior to discharge); prior to the pegloticase infusion and after the end of infusion (prior to discharge) at the Weeks 2, 6, 14, 21, 24, 36, End of Pegloticase Infusions Visit (if applicable) and Week 52/End of Study/Early Termination Visits. NOTE: Week 21 Visit and the End of Pegloticase Infusions Visit (if applicable) and Week 52/End of Study/Early Termination Visits are non-infusion visits.

Blood samples for MTX polyglutamate analysis will be collected prior to the pegloticase infusion on Day 1 and at the Weeks 14, 24 and 36 Visits during the Pegloticase + IMM Period .

The following presentations of subject pegloticase and MTX polyglutamate concentration data covered in this SAP will be provided:

This document is confidential.

- A listing including subject, week/time point (actual, planned), treatment and serum concentrations. End of infusion sampling times are expressed relative to the start time of infusion.
- A table summary of pegloticase and MTX polyglutamate concentrations at each time point (n; mean, SD, coefficient of variation (CV)% calculated as  $100\% \times SD/mean$ , minimum, 25th percentile, median, 75th percentile and maximum) for the PK Population or MTX Population, respectively.

Concentrations below the limit of quantification (BLQ) collected on Day 1 pre-dose will be summarized as zero. For the summary of pegloticase concentrations, all other concentrations BLQ will be imputed as half of the lower limit of quantification value. For the summary of MTX polyglutamate concentrations, all post-baseline concentrations BLQ will be excluded from analysis. The number of BLQ values will be presented for pegloticase and MTX summaries.

Concentrations for pegloticase will be summarized by treatment group for the PK Population. Further, the mean and CV% of pegloticase concentrations will be provided by visit and by treatment group in the subset of subjects who are ADA positive (defined as positive for anti-PEG or anti-uricase antibodies at any visit during the study) and ADA negative (defined as negative for both anti-PEG and anti-uricase antibodies for all visits during the study) for each visit.

Concentrations of MTX polyglutamate are measured for 5 active metabolites (MTX-PG1, MTX-PG2, MTX-PG3, MTX-PG4, MTX-PG5). Concentrations will be summarized for each of the individual metabolites, the sum of MTX-PG1 and MTX-PG2, the sum of MTX-PG3, MTX-PG4, and MTX-PG5, the sum of MTX-PG4 and MTX-PG5, and the sum over all 5 metabolites will be summarized for the MTX Population overall and by Month 6 sUA responders and non-responders. The mean PG3 and PG3-5 concentrations over time, by Month 6 sUA responder subgroup will be plotted.

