19. For all subjects, serum samples for PK analysis will be collected after the end of infusion on Day 1 (prior to discharge); prior to the pegloticase infusion and after the end of infusion (prior to discharge) at the Weeks 2, 6, 14, 21, 24, 36, End of Pegloticase Visit and Week 52/End of Study/Early Termination visits. NOTE: Week 21 Visit and the End of Pegloticase Infusions Visit (if applicable) and Week 52/End of Study/Early Termination Visits are non infusion visits.

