After Day 1, if a subject becomes unable to tolerate MTX or placebo for MTX, the MTX or placebo for MTX dose may be reduced and/or discontinued based on pre-defined criteria, and the subject may remain in the study.

The Investigator will review the clinical status and individual subject treatment goals (Appendix 17.4) at Screening, Week 24, Week 52 and the End of Pegloticase Infusions Visit (if applicable) or the Week 52/End of study/Early Termination Visit.

After the Week 52 Visit (or End of Pegloticase Infusion Visit [if applicable]), subjects should resume regular care for gout per the judgment of the treating physician, including resumption of urate lowering therapy (ULT) upon pegloticase discontinuation, if appropriate. Subjects will have a 3 and 6 Month Follow-up visit to assess clinical status, including sUA levels.

Subjects who receive at least one dose of MTX or placebo for MTX and are females of childbearing potential will receive a safety follow-up phone call/e-mail approximately 30 days after the last dose of MTX or placebo for MTX to verify at least one ovulatory cycle has occurred after the last dose of MTX or placebo for MTX. If the subject has not ovulated, a urine pregnancy test will be performed. Subjects who receive at least one dose of MTX or placebo for MTX and who are non-vasectomized males, will be asked, 3 months after MTX or placebo for MTX discontinuation, regarding partner pregnancy.

Samples for measurement of sUA levels, PK analysis of pegloticase, pegloticase immunogenicity and MTX Polyglutamate analysis will be collected at visits indicated in the Schedule for Assessments ([Section 2.1](#)).

Safety assessments, including monitoring and recording of all AEs, whether or not drug-related, measurement of vital signs, physical examinations, and monitoring of hematology and blood chemistry, will be performed.

[figure not shown]
The total blood volume to be collected from each subject during this study is approximately 910 mL.

An external Data Monitoring Committee (DMC) will be convened to review data for safety and efficacy with timing and criteria outlined in the DMC Charter, with the possibility of DMC recommendation on study design modification per criteria also to be outlined in the Charter.

An independent external adjudication committee will review reported events of infusion reactions, cardiovascular events and anaphylaxis.

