### **9.5.3 Pharmacokinetic and Anti-drug Antibody Measurements**

Serum samples for PK analysis of pegloticase will be collected after the end of infusion on Day 1 (prior to discharge); prior to the pegloticase infusion and after the end of infusion (prior to discharge) at the Weeks 2, 6, 14, 21, 24, 36, End of Pegloticase Infusions Visit (if applicable) and Week 52/End of Study/Early Termination Visits. **Note:** Week 21, End of Pegloticase Infusions Visit and Week 52/End of Study/Early Termination Visits are non infusion visits.

Serum samples for evaluation of anti-PEG and anti-uricase IgG antibodies will be collected prior to the pegloticase infusion on Day 1 and at the Weeks 2, 6, 14, 22, 24, 36, and at the non-infusion End of Pegloticase Infusions Visit (if applicable) or the Week 52/End of Study/Early Termination Visit and Month 3 Post Treatment Follow-up Visits.

Blood samples will be collected prior to the pegloticase infusion on Day 1 and at the Weeks 14, 24 and 36 Visits during the Pegloticase + IMM Period for MTX Polyglutamate analysis.

Each sample collection date and time will be recorded in source documents and the eCRF.

Detailed instructions regarding blood sample timing and handling are provided in the Laboratory Manual.

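### MTX polyglutamate values below quantification become zero on Day 1 but are dropped at Weeks 14, 24 and 36, so any such values create an apparent rise in the descriptive exposure summaries

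*SAP*

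**What the plan says.** SAP section 10.2 gives three rules for BLQ concentrations in one paragraph.

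- Day 1: "Concentrations below the limit of quantification (BLQ) collected on Day 1 pre-dose will be summarized as zero".
- Pegloticase after that: "For the summary of pegloticase concentrations, all other concentrations BLQ will be imputed as half of the lower limit of quantification value".
- Polyglutamates after that: "For the summary of MTX polyglutamate concentrations, all post-baseline concentrations BLQ will be excluded from analysis".

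The sampling plan is in the same section: "Blood samples for MTX polyglutamate analysis will be collected prior to the pegloticase infusion on Day 1 and at the Weeks 14, 24 and 36". Protocol section 9.5.3 agrees.

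The planned output is descriptive. It tabulates n, mean, SD, CV%, quartiles, median and range at each time point. For polyglutamates this covers five metabolites and several sums, in the MTX Population overall and by Month 6 responder status. Mean PG3 and PG3-5 are plotted over time by responder status. The number of BLQ values will be shown. SAP section 5.1 defines the MTX Population as anyone with at least one MTX dose. That includes subjects later randomized to placebo, and section 10.2 does not split the polyglutamate results by arm.

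**The concern.** The Day 1 sentence names no analyte, but pegloticase is first sampled after the Day 1 infusion (Protocol section 2.1, footnote 19; SAP section 10.2). The only scheduled Day 1 pre-dose concentration is therefore the polyglutamate one. Zero is a natural choice for a sample taken before any exposure, but this sample is not one: every subject starts MTX 15 mg weekly at Week -6.

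The same analyte is thus scored as zero when unmeasurable on Day 1 and deleted when unmeasurable later. A reader of the tables or plots would see a rise after Day 1 that the rule itself can produce.

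Deletion is also unlikely to be neutral. After Day 1, Protocol section 9.1 says that "the MTX or placebo for MTX dose may be reduced and/or discontinued based on pre-defined criteria, and the subject may remain in the study". Subjects who reduce or stop MTX but stay on infusions are still sampled and are the likely source of low values. Dropping them trims the low-exposure end of the comparison meant to relate MTX exposure to response.

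The SAP treats other analytes differently. A BLQ sUA is zero at every visit (section 9.1), and out-of-range safety laboratory results keep their numeric limit (section 11.4).

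**Working it through.** **Inputs.** The BLQ rules and visits come from SAP section 10.2. Arm sizes (90 and 45) and planning response rates (71% and 43%) come from SAP section 3.6. The documents give no BLQ share, assay limit or variability for polyglutamates, so there is no plan figure to reproduce. Those three quantities are assumptions below.

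**Step 1: direction.** Every excluded value lies below the lower limit of quantification (LLOQ), and every retained value lies at or above it. The mean after exclusion is therefore above the true mean whenever at least one value is BLQ. Replacing BLQ values by zero puts the Day 1 mean below the true mean. Neither statement needs a distribution.

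**Step 2: size of the artefact.** Take N samples per visit, a BLQ share f, and mean M of the quantifiable values, with nothing changing between visits.

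- Day 1 mean = [fN × 0 + (1 − f)N × M] / N = (1 − f)M
- Later mean = (1 − f)N × M / [(1 − f)N] = M
- Later / Day 1 = 1/(1 − f)

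| f | 1/(1 − f) | Apparent rise |
|---|---|---|
| 0% | 1.000 | none |
| 5% | 1/0.95 = 1.053 | +5.3% |
| 10% | 1/0.90 = 1.111 | +11.1% |
| 20% | 1/0.80 = 1.250 | +25.0% |
| 30% | 1/0.70 = 1.429 | +42.9% |

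**Step 3: bias against the true mean.** This used 2 million simulated lognormal values with the LLOQ placed at the f-quantile. Each cell shows CV 50%, then CV 100% (both assumed).

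| f | BLQ = 0 (Day 1 rule) | BLQ excluded (later rule) | BLQ = LLOQ/2 |
|---|---|---|---|
| 5% | −1.7%, −0.7% | +3.5%, +4.6% | −0.7%, −0.2% |
| 10% | −4.0%, −1.7% | +6.7%, +9.2% | −1.5%, −0.5% |
| 20% | −9.5%, −4.7% | +13.2%, +19.1% | −3.4%, −1.2% |

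The two steps agree: at f = 10% and CV 50%, 1.067/0.960 = 1.111.

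**Step 4: effect of a common rule.** With zero throughout, or LLOQ/2 throughout, both visits have the same expected mean when nothing changes. The ratio is 1.00 for every f.

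**Step 5: why a common rule is not enough without a split by arm.** Suppose all 135 subjects are sampled, placebo-arm values are near zero after washout, and the MTX-arm level m is unrelated to response.

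- Responders: 90 × 0.71 = 63.9 on MTX and 45 × 0.43 = 19.35 on placebo, 83.25 in total. Pooled mean = 63.9m/83.25 = 0.77m.
- Non-responders: 90 × 0.29 = 26.1 on MTX and 45 × 0.57 = 25.65 on placebo, 51.75 in total. Pooled mean = 26.1m/51.75 = 0.50m.

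The non-responder mean would be 34% lower (1 − 0.504/0.768) with no exposure-response relation at all. Restricting the comparison to the MTX arm removes this.

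**The case against.** **Mitigation already planned.** The BLQ count will be presented, along with n, median, quartiles and subject listings. For a single metabolite, if counts are shown by visit, a reader can recover the mean on the Day 1 rule as mean × n/(n + BLQ). No change-from-Day-1 analysis of polyglutamates is specified. This stands. It discloses the inconsistency but leaves the tabulated means and plotted curves uncorrected.

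**Other exposure data.** A reader might infer that polyglutamates are the trial's only measure of MTX exposure. They are not. SAP section 11.1 summarizes dosing duration, cumulative and average dose, dose reductions, and subjects without MTX or placebo between infusions. SAP section 11.2 adds capsule-count and diary compliance. Polyglutamates are the only concentration measure.

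**Large pooled effects.** A reader might infer a 50% rise in the pooled summary: with placebo at 45/135 and wholly BLQ at every visit, 1/(1 − 1/3) = 1.50. If placebo Day 1 levels were instead half the MTX-arm level, the rise would be m/[(2 + 0.5)m/3] = 1.20, and the zero rule would play no part. Both figures rest on mixing the arms and on placebo values that the documents do not give.

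**Lost non-responders.** Polyglutamate sampling ends when infusions end (Protocol section 9.3.3.1.1), so subjects who met the sUA stopping rule leave these summaries whatever the BLQ rule. The rule can be blamed only for low-exposure subjects who remain on pegloticase.

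**Sums.** It is tempting to say that sums will have different components in each subject. The SAP does not say how a BLQ component enters a sum, so the fault is silence. Protocol section 9.6.6 also defers details to a separate PK analysis plan, which was not available for this review.

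**Conclusion.** The inconsistency is real, and its direction follows from algebra. If any polyglutamate values are BLQ, the Day 1 mean is biased down, the Week 14, 24 and 36 means are biased up, and the rule alone yields a rise of 1/(1 − f): +11% at f = 10%, +25% at 20%. This assumes the same distribution and BLQ share at each visit. It also reads Day 1 as the polyglutamate baseline. SAP section 6.2.1 does not list the analyte, but no pre-MTX sample is scheduled. If no values are BLQ, the effect is zero.

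Exclusion also takes low-exposure MTX-arm subjects still on pegloticase out of the responder summaries and the PG3 and PG3-5 plots.

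The consequence is confined to descriptive exposure tables and plots. A reader might infer that the efficacy conclusions are at risk. They are not, because no primary or secondary test uses these values. The change is worth making because it is cheap and because these plots are where a relation between MTX exposure and response would be looked for.

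**What to change.** In SAP section 10.2:

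1. Use one BLQ rule for polyglutamates at all four visits: LLOQ/2 for each metabolite before any sum is formed, as already used for pegloticase. Remove the Day 1 zero rule for this analyte.
2. Produce the summaries, the responder comparison and the plots by randomized arm. Restrict the responder comparison and the PG3 and PG3-5 plots to the MTX arm, so that washed-out placebo subjects do not create a false exposure-response gap.
3. Show n and the percentage BLQ per visit and arm. Where more than half the values are BLQ, rely on the median and the percentage quantifiable instead of the mean.

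The cost is some SAP wording, a small amount of extra programming and somewhat lower reported means. LLOQ/2 leaves a small downward bias in the scenarios above (0.5% to 1.5% at f = 10%, 1.2% to 3.4% at f = 20%), but it is the same at every visit when the BLQ share is the same. Items 1 and 2 should be adopted together, because item 1 alone on the pooled population could produce the gap shown in step 5.
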